- Subject will instructed upon discharge to monitor their blood glucose values closely for approximately 24 hours post discharge. The contact information for the covering provider will be given to the subject.

V. e. Response to adverse events

Euphoria, sedation, ataxia, nausea, vomiting, delayed reactions, impaired memory, blurred vision, impaired fine muscles and dizziness might occur with blood alcohol content (BAC) of 0.1. If patient wants to stop receiving the ethanol infusion they can withdraw at any time.

Nausea is a potential side effect of glucagon administration. Minimal nausea was noted in clinical trials of the bi-hormonal closed-loop system in which up to 80 mcg of glucagon was given at intervals of as little as 5 minutes. The mean glucagon dose in these trials was ~1 mg over 24 hours. Therefore, we do not anticipate significant nausea associated with one 50 mcg doses of glucagon. However, if nausea is experienced by subjects, they are allowed up to 8 mg of ondansetron every 8 hours.

If vomiting occurs, a study physician or nurse practitioner will be notified. If the glucagon dose has already been given at the time of vomiting, then the experiment will be completed if the subject is willing since completing the experiment will not involve administration of more glucagon. If the vomiting occurred prior to glucagon injection, and may therefore be related to pre-existing illness or to ethanol, a study physician or nurse practitioner will assess if the study needs to be stopped prior to the glucagon administration. The subject may withdraw at any point of the study.

V. f. Supervision by Study Staff

A study physician or nurse practitioner will order all changes to the insulin infusion and glucose infusion rates and to the ethanol infusion, and will be on site at all times once the clamp has begun and until it is ended.

VI. Biostatistical Analysis

VI. a. Data Collected

At the time of enrollment:

- Age
- Sex
- Race and ethnicity
- Urine HCG for female volunteers
- Date of diabetes diagnosis
- Medical, surgical, and social history, allergies, and review of systems relevant to inclusion and exclusion criteria
- Date of last menstrual period in female volunteers
- Medications (prescription and non-prescription) and date of last change in medication regimen
- Duration of insulin pump use
- Insulin regimen (basal rate, sensitivity factor, and carbohydrate ratio)
- Average total daily dose of insulin in the last 30 days (from pump history)
- Height and weight
- Blood pressure
- Hemoglobin A1c
- Hemoglobin
- Creatinine and estimated GFR
- Serum Albumin
- Aspartate aminotransferase (AST)
- Alanine aminotransferase (ALT)
- Fractionated metanephrines (in subjects with history increasing the risk for a catecholamine secreting tumor)
- Free fatty acids

During the hyperinsulinemic-normoglycemic clamp:

- Venous BG measurements
- Timing and size of glucagon dose
- Insulin infusion rate
- Glucose infusion rates

- Ethanol infusion rate
- BAC according to breath alcohol meter
- BAC according to blood alcohol measurement
- Plasma insulin levels during the hyperinsulinemic-normoglycemic clamp
- Plasma glucagon levels during the hyperinsulinemic-normoglycemic clamp
- Any adverse events

VI. b. Study Endpoints

Primary endpoint analysis:

- Area over the curve for the glucose infusion rate in the hour following a subcutaneous glucagon dose (AOC_{GIR}) with a blood alcohol content of 0 vs. approximately 0.1%

Secondary endpoint analyses:

- Maximum change in GIR from baseline after glucagon injection in the presence and absence of ethanol

We will calculate means, median, percentages, standard deviations, standard errors, inter-quartile ranges, and 95% confidence intervals in descriptive analyses. We will use paired t-test for comparison of means. We will use multivariate regression models with repeated measurements to compare means and percentages while adjusting for patient demographics characteristics such as age, gender, body mass index, and body surface area.

VI. c. Power Analysis

Assuming that the standard deviation in each arm is 20% of the mean, and a within-patient correlation of 0.5, a sample size of 15 achieves 95% power to detect equivalence when the margin of equivalence is from -20% to 20% assuming the actual mean difference is zero. The significance level (α) is 0.05 using two one-sided paired t-tests. These results are based on 2000 Monte Carlo samples.

VII. Risks and Discomforts

There is a potential risk of nausea or vomiting in volunteers due to the administration of exogenous glucagon. The experiments, however, involve small subcutaneous glucagon doses. The recommended dose of glucagon for treatment of severe hypoglycemia in an adult with diabetes is 1000 mcg, given as a single subcutaneous or intramuscular injection. In practice, a smaller dose of 500 mcg is sometimes used initially to reduce the risk of nausea and vomiting. The total dose to be administered in our study is 50 mcg.

There is a risk of euphoria, sedation, ataxia, vomiting, delayed reactions, impaired memory, blurred vision, impaired fine muscles and dizziness with infusion of ethanol to achieve a blood alcohol content (BAC) of 0.1. We will exclude without previous alcohol exposure comparable to the study amount to avoid severe reactions. If patient wants to stop receiving the ethanol infusion they can withdraw at any time.

There is a risk of headaches, fatigue, malaise, and constipation with administration of ondansetron. Subjects will only be given this medication upon their request for nausea or vomiting.

There is a potential risk of hypoglycemia, since exogenous insulin will be administered. Given frequent BG monitoring (every two to five minutes), corresponding adjustment of a continuous dextrose infusion, and direct supervision by an NP or MD at all times, the risk of a hypoglycemic episode leading to significant harm to volunteers is expected to be very low. We do not expect to see a wide range of BGs. If two consecutive measurements are more than 250 mg/dL or less than 60 mg/dL the study provider will be informed and the clamp infusions will be checked. A small meal will be provided to subjects after completion of the study.

There is a theoretical risk of infection associated with the use of albumin, a protein purified from donated blood. The risk of transmitting disease is reduced by testing blood donors for infections, and by heat treating and purifying the albumin. Because of these measures, the risk is considered to be very small; no cases of disease transmission have ever been identified for albumin.

Subjects may experience mild discomfort associated with the insertion of the infusion into the SC tissue. Any discomfort is expected to be similar to that associated with injection of insulin. Once the infusion set is in place, there should be no significant discomfort. The risk for developing inflammation in the SC tissue at the insertion site is expected to be extremely low.

Subjects may experience discomfort with insertion of the peripheral intravenous line and the risks of intravenous lines remaining in place for about 10 hours include thrombosis and phlebitis of the peripheral vein.

Subjects may also experience mild discomfort associated with the subcutaneous injection of glucagon.

There is a risk of risk of dizziness or lightheadedness from blood loss. However, typical blood loss will be ~200 ml and loss of blood will be limited to no more than 400 ml.

VIII. Potential Benefits

The data derived from this study will allow us to determine if there is a significant reduction in glucagon effectiveness in the presence of alcohol or not. This will be important information to give to users of the bionic pancreas. If glucagon effectiveness does decrease, this information will be important for users of the bionic pancreas. If it does not, this means that the bionic pancreas will provide an even larger margin of safety over usual care when people with type 1 diabetes chose to consume alcohol. There is no direct benefit for the subject participating in this study.

IX. Data and Safety Monitoring

IX. a. Monitoring of Source Data

The principal investigator (PI), a study clinical research fellow (physician), or a study nurse practitioner will review the eligibility of each volunteer based on the case report from the screening visit.

All data from study visits will be combined in a single database that will be compared against the primary data files for integrity. The computer database will be backed up at least monthly and the backup media stored in a secure location.

The study will be conducted by the staff of the MGH Diabetes Research Center (DRC) in cooperation with the staff of the CRC. The PI will conduct meetings with study staff at least twice a month to review study progress, discuss any issues in study conduct, and review procedures. Study staff will be encouraged to raise any concerns they may have or problems they have identified at these meetings. The PI will decide a course of corrective action, and resolution or progress will be assessed no later than the next bimonthly meeting. An audit of procedures, regulatory documentation, and a sample of volunteer files will be performed by a member of the DRC at least biannually. The audit will be conducted by a DRC staff member not directly involved in the conduct of the study. This audit will include a review of regulatory documentation, such as IRB correspondence, and a review of files, including a review of consents, case report forms, and other data from study visits.

A numeric code will be substituted for the volunteers personal identifying information in the study database, which will be password protected. The key linking the medical record number of the volunteer with the numeric code, along with case report forms, and all information that is personally identifiable, will be kept in a locked filing cabinet in an investigator's locked office. All electronic records will be kept in a password protected computer database. All printed computer data will be disposed of confidentially when no longer needed. Only the study staff will have access to the study database. Subjects may not withdraw

from the de-identified database, but they may elect to have the key linking their medical record to the de-identified database destroyed.

The study data may be shared with collaborators outside of Partners, but only in a form in which all personally identifiable information has been removed. Shared data will be in the form of a database in which only a number identifies volunteers.

IX. b. Safety Monitoring

A study physician or nurse practitioner will directly supervise each experiment. The PI will be informed of any adverse events immediately and will make any adjustments to the study protocol as needed to maintain subject safety.

The Research Pharmacy will mix the insulin and ethanol solution. The calculations for the insulin infusion rate and the mixing of the insulin solution will be done in advance and checked by another physician or nurse practitioner. The calculations for the alcohol infusion rate will be done in advance and checked by another physician or nurse practitioner.

This study will be conducted under an Investigational New Drug application sponsored by the PI.

This study is considered moderate risk. The Principal Investigator and co-investigators will evaluate each experiment. Unanticipated problems, including adverse events, will be reported to the Partner's IRB in accordance with the PHRC policy on Unanticipated Problems Involving Risks to Subjects or Others including adverse events. An external Data and Safety Monitoring Board will oversee the conduct of the study and review its results on a regular basis. Additionally, the DSMB will be informed after any experiment that has to be discontinued due to hypoglycemia, hyperglycemia, or any unexpected adverse event. DSMB review will occur before any further experiments are performed. The DSMB will be informed if there are any changes to the study protocol that could significantly impact the safety or scientific validity of the study. A final DSMB meeting will convene after the completion of the study. After the first DSMB meeting, subsequent meetings may be convened via e-mail or conference call. Safety and efficacy data will also be reported to the FDA in compliance with applicable regulations.

IX. c. Adverse Event Reporting Guidelines

The PI will review any adverse events after each experiment. Adverse events will be reported to the Partner's IRB, the DSMB, and to the FDA.

X. Subject Compensation

Financial compensation of \$50 will be provided to all subjects who complete a screening visit. Subjects will be compensated \$200 after completion of each visit for a total of \$450 for the entire study.

XI. References

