We will test the effectiveness of glucagon in raising blood sugar in the absence of ethanol and in the presence of defined blood alcohol content (BAC) levels in a random-order crossover design. An established alcohol infusion algorithm for a clamp study will be used (10). If there is a significant reduction in glucagon effectiveness in the presence of alcohol, this will be important information to give users. If glucagon remains equally effective in the presence of alcohol, this means that the bionic pancreas will provide an even larger margin of safety over usual care when people with type 1 diabetes chose to use alcohol because of the increased risk associated with the use of alcohol in usual care. Since the alcohol levels to be tested are relatively high, if there is no effect at these levels we can be confident that the lower alcohol levels associated with healthy consumption of alcohol (2 drinks a day or less) will have no effect on the effectiveness of the bihormonal bionic pancreas.

II. Hypothesis and Specific Aims

We hypothesize that a BAC of 0.1 will not significantly alter the anti-hypoglycemic effect of micro-dose glucagon.

The specific aim of this study is:

Aim 1. To quantify the effect of a blood alcohol content on the anti-hypoglycemic efficacy of glucagon using a hyperinsulinemic-normoglycemic clamp technique in volunteers with type 1 diabetes in a random-order crossover trial.

III. Subject Selection

III. a. Inclusion Criteria

- Age 21 to 80 years old with type 1 diabetes for at least one year.
- Diabetes managed using an insulin infusion pump using rapid-acting insulin such as insulin aspart (NovoLog), insulin lispro (Humalog), or insulin glulisine (Apidra) for at least one week prior to enrollment.
- Alcohol exposure on at least one occasion in the last year consisting of at least 4 drinks in one sitting.

III. b. Exclusion Criteria

- Unable to provide informed consent.
- Unable to comply with study procedures.
- Unable to refrain from the consumption of alcohol at least 24 hours prior to study start
- Current participation in another diabetes-related clinical trial that, in the judgment of the principle investigator, will compromise the results of the clamp study or the safety of the subject.
- Pregnancy (positive urine HCG), breast feeding, plan to become pregnant in the immediate future, or sexually active without use of contraception.
- Aldehyde dehydrogenase deficiency as determined by a screening questionnaire

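### The trial is sized on an equivalence test with a ±20% margin (VI.c), but the endpoint analysis (VI.b) carries over no equivalence test, margin or decision rule for AOC_GIR

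*Combined protocol and SAP*

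**What the plan says.** Section VI.b (Study Endpoints) makes the primary endpoint the area over the glucose infusion rate curve in the first hour after glucagon (AOC_GIR), compared between the ethanol and no-ethanol visits. One general sentence covers the comparison for primary and secondary endpoints alike: "We will use paired t-test for comparison of means". VI.b also lists descriptive statistics, including "inter-quartile ranges, and 95% confidence intervals in descriptive analyses", and a repeated-measures regression adjusted for age, gender, body mass index and body surface area.

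Section VI.c (Power Analysis) is built on a different question. Its inputs are "Assuming that the standard deviation in each arm is 20% of the mean, and a within-patient correlation of 0.5". Its result is that "a sample size of 15 achieves 95% power to detect equivalence when the margin of equivalence is from -20% to 20" percent, with a true difference of zero. Its test is stated too: "The significance level (α) is 0.05 using two one-sided paired t-tests".

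The hypothesis in Section II reads "We hypothesize that a BAC of 0.1 will not significantly alter the anti-hypoglycemic effect of micro-dose glucagon". Section VIII says that the data will "determine if there is a significant reduction in glucagon effectiveness in the presence of alcohol or not", and ties the favourable message for device users to the negative answer. Section I.b ties the same message to equality: "If glucagon remains equally effective in the presence of alcohol, this means that the bionic pancreas will provide an even larger margin of safety".

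**The concern.** An equivalence claim needs a margin and a test that can fail when the data are imprecise. VI.c has both, but only as inputs to the sample size. VI.b, the text an analyst would follow, does not say that AOC_GIR is judged by that test, and it gives no rule for concluding equivalence. Neither subsection says which mean the 20% is a percentage of.

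An ordinary paired t-test asks whether the difference is zero. Failing to reject zero does not show that the difference is small. Because Sections II and VIII are phrased in terms of significance, a non-significant p-value could be taken as support for the hypothesis. What is at stake is a safety statement: that glucagon, and so the bihormonal device, keeps working when people with type 1 diabetes drink alcohol.

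**Working it through.** **Inputs.** From VI.c: arm SD 20% of the mean, within-patient correlation 0.5, n=15, margin ±20%, true difference 0, 0.05 for each one-sided test. From IV.a: 20 expected completers, 15 of them on a consistent protocol. The document does not say which set is analysed, so both sizes are shown.

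**1. The plan's power figure.**
- SD of the paired difference = 20% × √(2 × (1 − 0.5)) = 20%.
- Standard error = 20 / √15 = 5.16 percentage points.
- With 14 degrees of freedom t(0.95) = 1.761, so the 90% CI half-width at the planned SD is 1.761 × 5.16 = 9.1 points.
- TOST passes when the 90% CI lies inside ±20. Integrating that probability over the sampling distribution of the SD gives 95.8%. The stated 95% reproduces.
- The mean cancels here because SD and margin are both percentages, so the missing reference mean does not affect this figure.
- If the 95% CI named in VI.b were used as the equivalence interval (0.025 per side), power would be 89.8%.

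**2. What non-significance means under VI.b.** The two-sided paired t-test at 0.05 is non-significant when |t| ≤ t(0.975), which is 2.145 on 14 degrees of freedom. (VI.b gives no significance level; 0.05 is taken from VI.c.) With no true difference this happens in 95% of trials at any SD. For a true loss of 20%, t follows a noncentral t distribution with noncentrality 20 / (SD/√n); at the planned SD and n=15 that is 20 / 5.16 = 3.87.

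The documents give no basis for an SD above or below 20%, so the other rows are an assumed range. TOST uses a fixed ±20% margin.

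| SD of paired difference | 20% loss non-significant, n=15 | Same, n=20 | 20% loss passes TOST, n=15 | No difference passes TOST, n=15 |
|---|---|---|---|---|
| 15% | 0.2% | under 0.1% | 5.0% | 99.9% |
| 20% (plan) | 5.1% | 1.1% | 5.0% | 95.8% |
| 25% | 17.9% | 7.6% | 5.0% | 80.6% |
| 30% | 32.9% | 19.3% | 4.9% | 58.2% |
| 40% | 56.2% | 43.5% | 3.6% | 19.9% |

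As the data get noisier, TOST becomes harder to pass, while a non-significant t-test becomes easier to obtain when a loss is real.

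A true 10% change at the planned inputs (noncentrality 10 / 5.16 = 1.94) is non-significant in 56% of trials. Ten percent lies inside the margin, so this is not an equivalence error, but it shows that non-significance does not mean no change.

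**3. The reference mean at analysis.** AOC_GIR has units, so ±20% must be turned into a margin or a ratio. One million simulated trials were run at the plan's inputs (normal data, no-ethanol mean 100, SD 20 in both arms, correlation 0.5, n=15). Pass rates:

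| Form of TOST | No difference | True 20% loss | True 20% gain |
|---|---|---|---|
| Margin fixed in advance | 95.8% | 5.0% | 5.0% |
| ±20% of the estimated no-ethanol mean, treated as known | about 95% | about 3.7% | about 6.8% |
| Ratio form (E − 0.8C above 0 and E − 1.2C below 0) | about 94% | 5.0% | 5.0% |

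E and C are a participant's ethanol and no-ethanol values. Check on the ratio form: SD of E − 0.8C = 20 × √(1 + 0.64 − 0.8) = 18.3, and SD of E − 1.2C = 20 × √(1 + 1.44 − 1.2) = 22.3. These give one-sided powers of 99.1% and 95.1%, consistent with about 94% jointly.

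**The case against.** The strongest reply is that VI.c follows VI.b directly and states the test, the level and the margin. TOST is made of paired t-tests, so the VI.b sentence could be shorthand for it, and the decision rule is standard once those three items are given. This stands in part: the equivalence design is in the document, and a reader who inferred that the trial has none would be wrong. The shorthand reading does not hold, because the same sentence also serves the secondary endpoint, carries no margin and makes no reference to VI.c.

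A reader might also infer that the sponsor intends to report p > 0.05 as equal effect. The documents do not say so. The hypothesis and the benefits paragraph are not analysis rules, Aim 1 is framed as quantifying the effect, and VI.b promises standard errors and confidence intervals that would show imprecision. What remains is that no sentence rules the misreading out.

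Finally, on the plan's own inputs the two approaches have nearly the same error at a 20% loss (5.1% and 5.0%); below the planned SD, or with 20 participants at that SD, the t-test's figure is lower. That is correct. The large percentages depend on an SD that the documents neither support nor exclude.

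**Conclusion.** The point holds as a gap between the design and the analysis text, and it should be fixed. Followed literally, VI.b cannot deliver the equivalence conclusion on which the trial was sized, and the wording of II and VIII leans towards a difference test.

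The documents do not support the stronger reading that error is inflated under the plan's assumptions. Excess error at the margin arises only if the SD of the paired difference exceeds plan: at SDs of 25% to 40%, a true 20% loss is non-significant in 17.9% to 56.2% of trials at n=15, or 7.6% to 43.5% at n=20, against at most 5.0% passing TOST. These figures assume normally distributed differences and a fixed margin. One part needs no assumption about the SD: with no true difference, a non-significant t-test occurs in 95% of trials and so carries no information on precision.

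The undefined reference mean is a smaller matter. It leaves the stated power intact and has to be settled only for the analysis.

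**What to change.** In VI.b:
- State that the primary analysis of AOC_GIR is the VI.c TOST, each one-sided test at 0.05 (equivalently, the 90% CI of the paired difference lies within the margin).
- Define ±20% relative to a stated reference, such as the no-ethanol mean.
- Conclude equivalence only if both one-sided tests succeed; otherwise report that equivalence was not shown.
- Label the two-sided paired t-test and the adjusted regression as secondary or supportive, and state that non-significance is not evidence of equivalence.

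In II and VIII, replace the language of significance with equivalence within ±20%.

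Optional: if the margin is a percentage of the estimated no-ethanol mean, use the ratio form, which keeps the error at 5% on each side. If the estimated mean is treated as fixed instead, say that the error is no longer 5% on each side.

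The cost is wording, plus a restatement of power in VI.c to about 94% if the ratio form is chosen. Sample size and margin are unchanged.

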Volunteers who fit the selection criteria will be considered as candidates for this study. Advertisements for the study will be posted at the MGH Diabetes Center and will be distributed in the weekly broadcast email of research studies seeking volunteers. We will post basic information about the trial along with contact information on our website www.artificialpancreas.org and the study will be posted on www.clinicaltrials.gov. We will also post information regarding the trial at online venues for people with type 1 diabetes, such as Glu (online community of the Type 1 Diabetes Exchange). We will also contact individuals who have previously inquired about participation in our studies and have asked us to have their contact information kept on file.

IV. Subject Enrollment

IV. a. Number of Subjects

It is expected that we will have 20 volunteers complete two full-length clamp experiments with 15 of those volunteer's using a consistent protocol. The experiments are expected to be completed over a time period of 4-6 months.

Up to 35 volunteers with type 1 diabetes will be enrolled. The upper bound is based on the expectation that some volunteers will be excluded after the screening visit and blood tests, the possibility that some qualified volunteers will not be able to complete an experiment for scheduling reasons, the possibility that some experiments may have to be discontinued before completion (e.g. due to inability to maintain IV access or subject withdrawal), and the likelihood that minor modifications to the protocol for adjustment of the GIR, alcohol infusion rate, or the insulin infusion rate may be required during the first 2-3 experiments.

IV. b. Enrollment Procedures

Prospective participants may be briefed by a study staff member by phone regarding the study procedure and the inclusion and exclusion criteria. Potential volunteers may be sent an informed consent document to review by email or post.

IV. c. Consent Procedures

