We will test the effect of glucagon in the absence and presence of ethanol in a random-order crossover design. We will give each volunteer two identical injections of glucagon, one with a blood alcohol content of approximately 0 at one visit and another with a BAC of approximately 0.1 at another separate visit.

In Both Visits

- Subjects will report to the Clinical Research Center (CRC) by approximately 7:00 AM in the fasted state from 10pm the previous night. Subjects will be asked not to take any bolus insulin after 4 am, but to keep their basal insulin running.
- A urine HCG test will be performed for all female subject who are able to become pregnant. If the test is positive, the PI will inform the subject of the test result and the visit will be cancelled.

- A dipstick drug test will be performed to ensure that subjects are not under the influence of benzodiazepines or barbiturates or opiates that could synergize with ethanol to cause central nervous system depression.
- A Breathalyzer measurement will be obtained prior to the start of the visit to ensure the subject is not under the influence of alcohol.
- Two intravenous (IV) catheter lines will be placed, one in each arm. The sampling IV will be placed on the dorsal surface of the hand or the forearm. The catheters will typically be 20 gauge or smaller.
- Blood will be drawn for measurement of hemoglobin A1c, creatinine and estimated GFR, alanine aminotransferase (ALT), aspartate aminotransferase (AST), serum albumin, and free fatty acids.
- Regular human insulin will be added to the solution of 2% human serum albumin in normal saline to allow an infusion rate of 5-20 ml/hr based on the desired hourly insulin dose. Mixing of the insulin infusate will be performed by the research pharmacy and the final desired insulin concentration will be communicated to the research pharmacy in advance of the visit. The range of insulin concentrations in the infusate are expected to be from 0.2-1.2 u/ml, depending on the mean basal insulin rate of the subject.

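### Optional, low-cost improvement: visit order is randomised but no planned analysis uses it; block the order and add a period term

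*Combined protocol and SAP*

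**What the plan says.** Section V.d (Hyperinsulinemic-normoglycemic Clamp) sets the design: "We will test the effect of glucagon in the absence and presence of ethanol in a random-order crossover design". Each subject has one visit with ethanol and one without.

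Section VI.b gives the comparison, "We will use paired t-test for comparison of means", and adds a repeated-measurements regression "adjusting for patient demographics characteristics such as age, gender, body mass index, and body surface area". Section VI.c bases the sample size on "the standard deviation in each arm is 20% of the mean, and a within-patient correlation of 0.5", with 15 subjects, an equivalence margin of ±20%, a true difference of zero and α = 0.05, "using two one-sided paired t-tests". It states 95% power.

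No section names a period, visit or sequence term, or says how the order list is built or balanced. Section IV.a expects "20 volunteers complete two full-length clamp experiments with 15 of those" to have followed a consistent protocol, and allows that "adjustment of the GIR, alcohol infusion rate, or the insulin infusion rate may be required during the first 2-3 experiments".

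**The concern.** In a two-visit crossover, responses may differ between the first and second visit for reasons unrelated to ethanol. Randomising the order makes this cancel on average. In one trial it cancels fully only if the two orders are equally frequent, and 15 subjects cannot split equally. The covariates listed in VI.b describe the subject and not the visit, so they cannot do the work of a period term.

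The trial hopes to show that alcohol leaves glucagon's effect unchanged, and Section VIII says the answer will go to users of the bionic pancreas. Wrongly declaring equivalence is therefore the costly error. A visit shift combined with unequal orders could raise that risk in the trial actually run. A shift also inflates the spread of the paired differences when it is not modelled.

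**Working it through.** **Inputs.** From VI.c: SD per arm 20% of the mean, correlation 0.5, n = 15, margin ±20%, α = 0.05 (taken as 0.05 per one-sided test), true difference 0. The size of any visit shift and the split of orders are not in the documents and are assumed below.

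**The plan's own figure.** SD of the paired difference = 20 × √(2 × (1 − 0.5)) = 20% of the mean. SE = 20/√15 = 5.16. The exact power of the paired equivalence test on 14 df is 95.8%, so the stated 95% reproduces.

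**Why the covariates do not help.** Let d = (ethanol response) − (non-ethanol response) within a subject. A main effect of age, sex, BMI or BSA adds the same amount to both responses and drops out of d. This is exact in a linear model with complete pairs. It is not exact with incomplete pairs or for percentages.

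**Effect of a shift.** Let π be the visit-2 minus visit-1 shift, with n₁ subjects in one order and n₂ in the other.

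- Without the term, the mean of d moves by π(n₁ − n₂)/15: π/15 at 8/7, π/5 at 9/6, π/3 at 10/5.
- The expected variance of d becomes σ² + (15/14)π²[1 − ((n₁ − n₂)/15)²]. At 8/7 with σ = 20 and π = 10 this is 400 + 106.7 = 506.7, an SD of 22.5.
- With the term, the shift is removed. The variance of the estimate is (σ²/4)(1/n₁ + 1/n₂) on 13 df. At 8/7 the SE is 20 × √(15/224) = 5.18.

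**Power.** Two readings of the SD in VI.c are possible. In A the shift comes on top of σ = 20. In B it is already inside, so the residual SD is √(400 − π²). Each cell gives power without → with the term, in %.

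| Split | Reading | π = 0 | π = 5% | π = 10% | Break-even π |
|---|---|---|---|---|---|
| 8/7 | A | 95.8 → 95.5 | 95.1 → 95.5 | 92.7 → 95.5 | 3.0% |
| 8/7 | B | 95.8 → 95.5 | 96.3 → 96.7 | 97.7 → 99.0 | 3.0% |
| 9/6 | A | 95.8 → 94.8 | 94.8 → 94.8 | 91.2 → 94.8 | 5.0% |
| 9/6 | B | 95.8 → 94.8 | 96.0 → 96.1 | 96.7 → 98.7 | 4.9% |
| 10/5 | A | 95.8 → 92.9 | 94.2 → 92.9 | 88.2 → 92.9 | 6.5% |
| 10/5 | B | 95.8 → 92.9 | 95.4 → 94.5 | 94.7 → 98.1 | 6.2% |

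**False equivalence at a true 20% loss, without the term.** Averaged over random order it is 5.0%. Given a 10/5 split it depends on the direction of the imbalance: 8.3 or 2.3% with a 5% shift and 11.4 or 0.8% with a 10% shift (A); 8.5 or 2.2% and 12.2 or 0.5% (B). At 8/7 it stays at or below about 5.2% for shifts of 3, 5 or 10%. With the term it is 5.0% throughout.

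**How likely each split is.**

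| Order list | 8/7 | 9/6 | 10/5 | 11/4 or worse |
|---|---|---|---|---|
| Simple randomisation of 15 | 39% | 31% | 18% | 12% |
| Random 15 out of 20 balanced 10/10 | 70% | 27% | 3% | – |

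A list in blocks of 4, restarted for the consistent-protocol cohort, gives 8/7 for the first 15 if nobody is lost. If 10, 20 or 30% (assumed) are lost at random and replaced by the next on the list, simulation gives 8/7 in 87, 73 or 64%, 9/6 in 12, 23 or 29%, and 10/5 or worse in about 1, 3 or 7%.

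**The case against.** The strongest reply is that the planned analysis is valid as it stands. Randomised order makes the paired comparison unbiased on average with 5.0% false equivalence, and the sample size is right. The documents give no visit effect and no reason to expect one. Section V.d standardises the visits closely, with the same fasting, glucose target, glucagon injection and infused volume. If the SD in VI.c already contains visit-to-visit variation, power stays near 95% without the term. Blocking alone does most of the work: at 8/7 with a 5% shift the term adds only 0.4 points. Under simple randomisation the term loses power on average unless the shift exceeds about 6.5%. The worst false-equivalence figures need a rare split, a large shift and an unfavourable direction.

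All of this stands, and it is why the point is optional. It does not remove the case for the change. Standardising visits does not exclude a visit effect, the order list is not described, and the expected reduction from 20 completers to 15 can unbalance even a balanced list. Two smaller points also stand. The covariate list is introduced with *such as*, so a period term is not ruled out, only not planned. And VI.b does not itself name the equivalence test; it appears only in VI.c.

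**Conclusion.** The point holds as a cheap improvement and not as an error in the sample size or the stated power. Under the assumptions in VI.c and an 8/7 split, a period term costs about 0.3 points of power if there is no visit shift and gains power above a shift of about 3% of the mean. With worse splits the break-even rises to about 5% (9/6) and 6 to 6.5% (10/5), but the protection against a displaced estimate matters more there. The benefit depends on a shift that the documents do not give, so its size cannot be settled from them. A period term does not deal with carry-over.

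**What to change.** 1. In VI.b, name the equivalence analysis of AOC_GIR against ±20% as primary, and fit it with treatment and period as fixed effects and subject as random.
2. In V.d, state that visit order comes from a concealed list in small blocks, for example of 4. Someone who does not enrol subjects should hold the list, because staff who see which infusion is given could guess the last places in a fixed block.
3. Start a fresh blocked list once the protocol is fixed after the first experiments, and say that balance may still not carry over exactly to the 15 analysed.

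The cost is a few sentences, an order list and one degree of freedom, with no extra subjects, visits or measurements. With no shift, power falls by about 0.3 points at 8/7, 1.0 at 9/6 and 2.9 at 10/5. If the list is balanced over 20 but not restarted, and a random 15 are analysed, the average fall is about 0.70 × 0.25 + 0.27 × 1.0 + 0.03 × 2.9 ≈ 0.5 points, and the break-even shift is 4.1% (A). Without blocking, the average fall is 2.2 points with no shift and 1.0 with a 5% shift (A), so the two changes belong together.
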